Participants with	Plasma lactate level	Larger effect of fluid	Test of interaction in
severe metabolic	above 4 mmol/l	restriction in severe	the adjusted analysis
failure	(yes/no)	metabolic failure	described above; P-
			value 0.01
Participant weight	Weight tertiles as	Larger effect of fluid	Test of interaction in
	observed in the 6S and	restriction with lower	the adjusted analysis
	TRISS trial cohorts	weight	described above; P-
	combined [2, 3]		value 0.01
IV fluid volume given	30 ml/kg or more	Larger effect of fluid	Test of interaction in
prior to randomisation	given (yes/no)	restriction with less	the adjusted analysis
		fluid given	described above; P-
			value 0.01

Table 3. The definitions of major protocol violations, the exclusion of which will form the perprotocol population

Intervention group	Major protocol violation definition
IV fluid restriction	IV fluids given without one of the extenuating
	circumstances occurring
Standard of care	No IV fluids given

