Definition of baseline variables

- -Sex: the genotypic sex of the participant
- -Age: defined in inclusion criteria
- -Date of admission to hospital: the date of admission to the first hospital the participant was admitted to during the current hospital admission
- -Date and time of admission to the ICU (or high-dependency or step-up/step-down beds; see inclusion criteria): the date of admission to the first ICU the participant was admitted to during the current hospital admission
- -From where was the participant admitted to ICU
 - Emergency department or directly from the pre-hospital setting:
 Accident/Emergency/Casualty/Acute department in the same or another hospital or direct admission to the ICU by an ambulance service or similar

The CLASSIC trial protocol Page 46/82

- Hospital ward: Any location in the same or another hospital not covered in the other 3 categories
- Operating or recovery room: including surgical theatre, endoscopy and angiography suite and any recovery facilities observing patients following invasive procedures.
- Another ICU: either within the same or another hospital

Focus of infection (documented or suspected):

- o Pulmonary: e.g. pneumonia, or empyema
- Gastrointestinal infection: e.g. primary, secondary or tertiary peritonitis, abscess, cholangitis, cholecystitis, or invasive diarrhoeal disease
- Urinary tract infection: e.g. urinary tract infection, or pyelonephritis
- o Skin or soft tissue infection: e.g. cellulitis, phlegmon, erysipelas, or fasciitis
- Other: other infectious focus documented or suspected including meningitis, endocarditis, osteomyelitis, arthritis and bacteraemia
- -Co-morbidities, must have been present in the past medical history prior to ICU admission and are defined as follows:
 - o Active hematologic cancer: defined in the stratification variables
 - o History of metastatic carcinoma: defined in the stratification variables
 - History of ischemic heart disease or heart failure: previous myocardial infarction, invasive intervention for coronary artery disease, stable or unstable angina, NYHA class 3 or 4 or measured LVEF < 40%.

 - Chronic dialysis: use of renal replacement therapy at least once a week e.g. chronic haemodialysis or haemofiltration, peritoneal dialysis
- Blood values, interventions and vital parameters:
 - o Participant weight: measured or estimated in kg
 - Highest plasma lactate value within the last 3 hours of randomisation: in mmol/L

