The estimates of the control event rates originate from data of previous septic shock trials.

We expect the following outcomes to be highly skewed (non-normally distribution): days alive without life support and out of hospital at day 90 and HRQoL and cognitive function at 1 year. As we lack sufficient knowledge on the details of the non-normal distribution no realistic power analysis can be provided. We therefore refrain from this in order to avoid creating a false impression of precision.

Pre-planned subgroup analyses

We plan to assess heterogeneity of intervention effects of the primary outcome in the following 5 subgroup analyses based on patient characteristics at baseline:

- 1. Respiratory support at randomisation (hypothesised increased effect of fluid restriction in patients receiving respiratory support)
- 2. Severe AKI defined as modified KDIGO2 or above⁷ at randomisation (hypothesised increased effect of fluid restriction in patients with severe AKI)⁷

- 3. Severe metabolic failure at randomisation defined as plasma lactate level above 4 mmol/l (hypothesised increased effect of fluid restriction in patients with severe metabolic failure)
- Participant weight at randomisation with higher weight defined as bodyweight (measured or estimated) ≥76 kg²⁰⁻²² versus lower weight as <76 kg (hypothesised increased effect of fluid restriction in patients with lower weight)
- Patients who received ≥30ml/kg body weight IV fluids in the 24 hours prior to randomisation versus patients who received a lower volume (hypothesised increased effect of fluid restriction in patients with less fluids given 24 hours prior to randomisation)

For all subgroups a P-value <0.01 in the test of interaction will be considered statistically significant. Detailed definitions of the subgroup analyses are available in the protocol.

Trial profile

At trial completion, the flow of trial participants will be reported according to the Consolidated Standards of Reporting Trials (CONSORT) statement.²⁶

Data Monitoring and Safety Committee

A Data Monitoring and Safety Committee (DMSC) has been formed, consisting of independent ICU trialists/clinicians and a biostatistician who collectively have experience in the management of ICU patients and in the conduct, monitoring and analysis of RCTs. The charter for the DMSC is available in the protocol.

Interim analyses

We will perform 3 interim analyses:

- 1. Interim analysis when 10% of patients have completed 30-days follow-up

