Participant weight	Bodyweight (measured or estimated) ≥76 kg versus lower weight as <76 kg ^{10–12}	Larger effect of fluid restriction with lower weight	Test of interaction in the adjusted analysis; P-value 0.01
IV fluid volume given 24 hours prior to randomisation	Patients who received ≥30 ml/kg body weight IV fluids prior to randomisation versus patients who received a lower volume Definition: Defined as all crystalloids (any saline, NaHCO3-, Ringer's and Plasmalyte™ solutions), colloids (albumin 4, 5 or 20%, gelatine, hydroxyethyl starch and dextran solutions) and blood products (units of red cells, plasma or platelets) the participant has received within the last 24-hours independent of location (in- or pre- hospital) including fluids with IV medication and IV	Larger effect of fluid restriction with less fluid given	Test of interaction in the adjusted analysis; P-value 0.01

nutrition. Intraosseous fluid will be counted as IV.	

3. References

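### The weight, lactate and prior-fluid interactions are tested only after two-way splits: add continuous tests, and align the protocol's leftover weight tertiles with the SAP's 76 kg

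*SAP*

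**What the plan says.** The SAP (Pre-planned subgroup analyses) lists five subgroups for 90-day mortality. Three come from measured baseline values, each split in two:

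- Lactate: "Severe metabolic failure at randomisation defined as plasma lactate level above 4 mmol/l".
- Weight: "higher weight defined as bodyweight (measured or estimated) ≥76 kg". Section 2 of the SAP appendix repeats it: "Bodyweight (measured or estimated) ≥76 kg versus lower weight as <76 kg".
- Prior fluid: "Patients who received ≥30ml/kg body weight IV fluids in the 24 hours prior to randomisation versus patients who received a lower volume".

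The threshold is common to all: "For all subgroups a P-value <0.01 in the test of interaction will be considered statistically significant". Neither document plans an interaction test with a continuous modifier.

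The underlying data are finer than the splits. Protocol Appendix 2 defines "Participant weight: measured or estimated in kg" and lactate in mmol/L, and section 9.2.2 lists the IV fluid volume over the 24 hours before randomisation.

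Protocol Table 2 (section 10.2) has the same lactate and fluid splits, but its weight row reads "Weight tertiles as" seen in two earlier trial cohorts combined, without cut values. The SAP adds, after listing its own definitions, "Detailed definitions of the subgroup analyses are available in the protocol".

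**The concern.** Protocol Table 2 and the SAP appendix expect a larger effect of restriction as weight falls and as less prior fluid has been given. Those are graded statements, and a graded term tests them most directly. A two-group test treats a patient just above the cut like one far above it, and discards information already collected. Interaction tests at P<0.01 have limited power in a trial sized for a main effect, so a non-significant result after splitting says little about whether the effect is homogeneous.

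The weight row adds a smaller problem. Three groups and two groups give different tests of one hypothesis, and the SAP's pointer leads back to the version it does not use.

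**Working it through.** **Reproducing the plan's own figure.** Neither document gives power for any interaction test, so the only figure to reproduce is the total N. With 45% versus 38% mortality, two-sided alpha 0.05, power 80% and pooled variance under the null:

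n per arm = [1.960 × √(2 × 0.415 × 0.585) + 0.842 × √(0.45 × 0.55 + 0.38 × 0.62)]² / 0.07² ≈ 777, total 1554. This matches the plan.

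**Information kept by grouping.** Assume a normal modifier and an interaction linear in log-odds. The information kept is then approximately the share of the modifier's variance lying between the groups. For a split with proportion p below the cut c = Φ⁻¹(p):

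efficiency = φ(c)² / [p(1 − p)]

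| Grouping | Calculation | Efficiency |
|---|---|---|
| 50/50 | 0.3989² / 0.25 | 0.64 |
| 40/60 | 0.3863² / 0.24 | 0.62 |
| 30/70 | 0.3477² / 0.21 | 0.58 |
| 20/80 | 0.2800² / 0.16 | 0.49 |
| Tertiles | (2/3) × (0.3636 / 0.3333)² | 0.79 |

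**Power.** Logistic interaction tests were simulated with N=1554, 1:1 allocation, 45% control mortality, a treatment log odds ratio of −0.278 (45% to about 38.25%) at the modifier's mean, a standard normal modifier without a main effect, two-sided alpha 0.01 and 2000 runs. Stratification variables were left out.

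| Interaction OR per SD | Continuous | Median split | 30/70 split | Tertiles, 2 df | Tertile trend, 1 df |
|---|---|---|---|---|---|
| 1.00 (null) | 1.0% | 1.3% | 1.0% | 1.0% | 0.8% |
| 1.22 | 28% | 16% | 14% | 15% | 22% |
| 1.35 | 62% | 39% | 34% | 38% | 49% |
| 1.49 | 89% | 67% | 60% | 68% | 79% |

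The two calculations agree. Power of 61.6% at alpha 0.01 implies a mean test statistic of about 2.576 + 0.295 = 2.871. Multiplying by √0.637 gives 2.291, hence power Φ(2.291 − 2.576) = 39%. Multiplying by √0.576 gives 2.178 and 34%.

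**Which weight definition applies.**

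- The SAP states 76 kg in its text and again in its appendix.
- The SAP opens by saying that analyses for the primary publication follow it, apart from listed changes, and that it was published before the interim analyses (version 1.0, July 2019).
- Its listed changes revisit the ventilation subgroup and leave weight alone.
- Protocol section 10 defers to the detailed SAP.
- The protocol change log shows version 2.4 altering only the substudy appendix, so the tertiles are carried-over text.

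**The case against.** The strongest defence concerns lactate and prior fluid, whose cuts have a basis in the documents. Protocol section 6.1 makes a lactate of 4 mmol/L or above one of the circumstances permitting IV fluid in the restrictive arm, so the treatment contrast may change near that value, and one linear term would blur such a step. The 30 ml/kg volume is the guideline volume cited in section 1.2. Both cuts are pre-specified with a stated direction and a strict threshold. This stands: replacing those two tests would be a trade-off, whereas adding a continuous test next to them loses nothing. It does not carry over to weight, where the SAP cites earlier trials but gives no reason for an effect change at 76 kg.

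Three stronger readings are tempting, and the documents do not support them.

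- A reader might infer that the weight test is undetermined, or open to choice once results are known. The SAP states 76 kg twice, was published in July 2019 before the interim analyses, and governs the primary publication.
- A reader might infer a fixed cost of (1 − 0.637) × 1554 ≈ 565 participants per test. That needs a normal modifier and a median split. The documents give no distributions and do not say that any cut is a median. Eligibility also truncates lactate (at least 2 mmol/L) and prior fluid (at least 1 L).
- A reader might infer that splits away from the median always lose more. That fails for skewed variables: for an exponential variable, a median split keeps 0.25 × (1.693 − 0.307)² = 48% of the variance, while cutting off the top 20% keeps 0.16 × (2.609 − 0.598)² = 65%.

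**Conclusion.** The point holds as a modest, inexpensive improvement. Three measured modifiers are tested only after two-way splits. Under a normal modifier and a linear interaction, that keeps about 49–64% of the information for splits from 20/80 to 50/50. At an interaction odds ratio of 1.35 per SD, it takes power from about 62% to 34–39% for 30/70 and median splits. These are illustrations under stated assumptions, since the documents supply no covariate distributions; the loss shrinks or vanishes if the effect truly changes at the chosen cut.

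The weight subgroup is inconsistently described across the two documents, but the SAP settles which definition applies. The consequence is confined to the subgroup findings. The SAP bases the trial's conclusion on the intention-to-treat analysis and lists the subgroup analyses among the sensitivity analyses.

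**What to change.** 1. Add to the SAP an interaction test with the continuous modifier (weight in kg, prior fluid in ml/kg, log lactate) in the model adjusted for the stratification variables, with a spline check of linearity.
2. Make the continuous test the main one for weight, and keep 76 kg for displaying estimates.
3. For lactate and prior fluid, report the continuous test alongside the pre-specified 4 mmol/L and 30 ml/kg tests, and keep those cuts for display.
4. If the data have already been analysed, label the continuous tests supplementary and leave the pre-specified cuts as the declared tests. The SAP's summary of changes dates the final analyses to March 2022, so this is probably the position.
5. Align the weight row of protocol Table 2 with the SAP's 76 kg, and point the SAP's cross-reference to its own appendix.

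The cost is a few lines of wording and no new data. The statistical price is a linearity assumption, which the spline can check, and two further formal tests. If independent, five tests at 0.01 carry a 1 − 0.99⁵ = 4.9% chance of at least one false positive, and seven carry 1 − 0.99⁷ = 6.8%. The true increase should be smaller, because the paired tests use the same modifier.

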Appendix to the CLASSIC trial statistical analysis plan, version 1.0, published in July 2019.

1.	Statistical analyses: significance level for the secondary outcomes
2.	Definitions of pre-planned subgroup analyses
3.	References

1. Statistical analyses: significance level for the secondary outcomes

We applied the methods as suggested by Jakobsen et al. ¹ As a full Bonferoni correction for multiple comparisons may be too conservative, a pragmatic approach is used dividing the pre-specified P-value threshold with the value halfway between 1 (no adjustment) and the number of primary outcome comparisons (Bonferroni adjustment).

As we have 7 secondary outcomes, the threshold for the P-value for these outcomes was calculated as follows:

0.05/ ((7+1)/2)= 0.0125

A full Bonferoni correction would equal a P-value as follows:

0.05/7 = 0.0071

We then chose the significance level of P 0.01 which is between the two corrections.

2. Definitions of pre-planned subgroup analyses

Heterogeneity of the intervention effects on the primary outcome will be analysed in the following subgroups based on baseline characteristics

Subgroup	Definition	Hypothesised direction	Statistical test
Participants who receive respiratory support	Respiratory support within the last 24 hours prior to randomisation(yes/no)	Larger effect of fluid restriction in patients who receive respiratory support	Test of interaction in the adjusted analysis; P-value 0.01
	Definition: Invasive or non- invasive mechanical ventilation including continuous mask CPAP or CPAP via tracheostomy within the last 24 hours prior to randomisation. Intermittent CPAP and high flow nasal cannula oxygen therapy are NOT considered respiratory support		
Participants with severe acute kidney injury	Modified KDIGO stage 2 or above ³ (yes/no)Definition: Modified KDIGO because we don't have urine output available at randomisation.Stage 2: p-creatinine 2.0-2.9*baseline Stage 3: p-creatinine 3.0*baseline or increase in to ≥354	Larger effect of fluid restriction in acute kidney injury	Test of interaction in the adjusted analysis; P-value 0.01

	mmol/l or initiation of RRT		
Participants with severe metabolic failure	Plasma lactate level >4 mmol/l (yes/no)	Larger effect of fluid restriction in severe metabolic failure	Test of interaction in the adjusted analysis; P-value 0.01
Participant weight	Bodyweight (measured or estimated) ≥76 kg versus lower weight as <76 kg ^{10–12}	Larger effect of fluid restriction with lower weight	Test of interaction in the adjusted analysis; P-value 0.01
IV fluid volume given 24 hours prior to randomisation	Patients who received ≥30 ml/kg body weight IV fluids prior to randomisation versus patients who received a lower volume Definition: Defined as all crystalloids (any saline, NaHCO3-, Ringer's and Plasmalyte™ solutions), colloids (albumin 4, 5 or 20%, gelatine, hydroxyethyl starch and dextran solutions) and blood products (units of red cells, plasma or platelets) the participant has received within the last 24-hours independent of location (in- or pre- hospital) including fluids with IV medication and IV	Larger effect of fluid restriction with less fluid given	Test of interaction in the adjusted analysis; P-value 0.01

nutrition. Intraosseous fluid will be counted as IV.	

3. References


Summary of changes to statistical analysis plan

Changes during conduct of the final statistical analyses in March 2022:

- The relative risks with 95% CIs of the primary outcome were computed by G-computation based on the logistic regression and not generalized linear models with log and identity links as the latter models did not converge.
- We specified that major protocol violations included both discontinuation or withdrawal from the trial protocol by patient, surrogate, clinician, or investigator AND violation of the IV fluid protocol. Patients having one of these violations were not included in the per-protocol population.
- We specified the planned subgroup of mechanical ventilation to include both invasive and non-invasive mechanical ventilation including continuous CPAP as this was the variable which had been collected in the baseline form throughout the trial period.
